4.2 Secondary

- To evaluate the complete response rate to panobinostat maintenance therapy after autologous HCT.
- To determine the 2-year PFS and OS of autologous HCT followed by panobinostat maintenance therapy in patients with multiple myeloma.
- **Exploratory secondary objectives:**
 - To evaluate histone acetylation (H3 and/or H4) of peripheral blood mononuclear cells
 - To isolate and identify clonotypic B cell progenitors in multiple myeloma patients from the bone marrow, peripheral blood and stem cell grafts.
 - To evaluate T-cell immune response against known myeloma tumor associated antigens while on panobinostat maintenance.
 - To evaluate humoral immunity against pneumococcal serotypes included in the standard of care heptavalent pneumococcal conjugate vaccine, and to assess cellular immune responses against CRM adjuvant found in the heptavalent pneumococcal conjugate vaccine.
 - To evaluate minimal residual disease (MRD) after autologous HCT followed by panobinostat maintenance therapy using flow cytometry
 - To evaluate MRD after autologous HCT followed by panobinostat maintenance therapy using multiplex PCR for CDR3 sequences

5 Overall study design

This is an open-label trial to determine the safety and tolerability of 2 different dosing schedules of single agent panobinostat maintenance therapy in patients with multiple myeloma who underwent high-dose melphalan followed by autologous HCT in patients with multiple myeloma. It is unknown whether the toxicity profile of panobinostat will be accentuated in patients after autologous HCT in the setting of maintenance therapy, hence the dose chosen for maintenance therapy is lower than MTD dosing or other phase 2 studies. There are 2 dosing schedules evaluated in this protocol in order to assess optimal tolerable schedule for panobinostat maintenance therapy after autologous HCT. As secondary

objectives, we will evaluate response after completion of treatment, and 2-year PFS and OS. As correlative studies, we plan to evaluate MRD, and to assess clonotypic B cells following an autologous HCT. We also plan to evaluate T effector immune response after autologous HCT while on panobinostat maintenance therapy.

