9.2 Assessment of immune response

Bone marrow research samples obtained (only for those who consent for screening research sample consents) will be analyzed to determine the presence of common multiple myeloma tumor associated antigens (TAAs) including survivin, WT-1, NY-ESO, and MAGE using immunohistochemistry (IHC) or polymerase chain reaction (PCR). Prior biopsy specimens may be requested if available, in order to perform IHC for the described TAAs. Research blood samples will be obtained prior to transplant, at baseline (prior to the initiation of maintenance), after 3 cycles of maintenance therapy, and after panobinostat maintenance

(after completing of therapy) to evaluate for the presence of T-cell precursors against individual patient's identified TAA using peptide pools.

As a standard of care, all autologous HCT recipients will receive heptavalent pneumococcal conjugate vaccine (PCV13, Prevnar™) at around 3 months from the time of transplant. We hypothesize that patients immunized with heptavalent pneumococcal conjugate vaccine, who then receive panobinostat maintenance therapy, may have augmented immune responses. (stan Each vaccine specific serotype IgG level will serve as a marker for immune response. We propose to measure following anti-pneumococcal IgG antibody serotype panel at baseline, at cycle #6 and after completion of maintenance (completion of 12 cycles) to assess immune reconstitution with panobinostat maintenance therapy. The antibody panel contains serotypes 1, 4, 5, 7F, 8, 9V, 9N, 12F and 18C. A positive response of IgG antibody is considered to be greater than or equal to 1 microgram/mL. Patients may also receive standard of care pneumococcal conjugate vaccine (usually at 6 months and 12 months after autologous HCT).

T cell response in the setting of panobinostat maintenance therapy will be evaluated at baseline, after cycle #3 and cycle #6, and after completion of maintenance therapy (completion of 12 cycles). Specifically we will measure the % of T1 cells and cytotoxic T cells specific for intracellular IFN-gamma production after co-culture of patients with T cells with the inactivated diphtheria conjugate (CRM197) which is a component of the pneumococcal conjugate vaccine.

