reproducible within each assay, so the frequency of each sequence after amplification can be computationally adjusted for the specific forward and reverse primer that amplified that clone, yielding a direct estimate of the frequency of each clonal CDR3 rearrangement in the starting template material. If the high-throughput sequencing is performed on a sample containing one million nucleated cells, then its sensitivity in that circumstance is estimated to be 1 in a million.

Sequencing CDR3 regions:

IGH CDR3 regions can be amplified and sequenced from DNA samples. Amplification and sequencing of *IGH* CDR3 regions will be carried out on the *ClonoSEQ*TM platform (Adaptive Biotechnologies, Seattle, WA). The sequences for *IGH* CDR3 regions are delineated according to the definition established by the International ImMunoGeneTics collaboration.^{105,106} A standard algorithm is used to identify which V, D, and J segments contributed to each *IGH* CDR3 sequence and which V and J segments contributed to each CDR3 sequence.^{105,106} Rearranged CDR3 sequences are classified as non-productive if insertions or deletions were identified that resulted in frame-shifts or premature stop-codons.

Bone marrow samples (with CD138 selected DNA) will be obtained prior to autologous HCT, prior to the initiation of HCT, at cycle #6 of maintenance and after completion of planned panobinostat maintenance therapy to evaluate myeloma clones. To identify index myeloma clones, archived FFPE bone marrow clot sections (prior to start of systemic chemotherapy) will be obtained at Moffitt Cancer Center.

Table 9-1 Research Sample Acquisition Schedule

	Pre-HCT	Pre-maintenance	Cycle #1 (days 1, 5)	Cycle #2	Cycle #3	Cycle #6	Cycle #9	End of study
Peripheral blood	1 tiger top/6 green top	1 tiger top/6 green top	1 tiger top/6 green top (day 1); 2 green top (day 5)	1 tiger top/6 green top	1 tiger top/6 green top	1 tiger top/6 green top	1 tiger top/6 green top	1 tiger top/6 green top
Bone marrow	1 tiger top/4 green top	1 tiger top/4 green top	-	-	-	-	-	1 tiger top/4 green top
Stem cell graft (Apheresis)	3mL in a 50mL falcon tube	-	-	-	-	-	-	-

10 Safety monitoring

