13.1 Statistical methods and data analysis

This is an open label study of 2 different panobinostat maintenance dosing schedules after autologous HCT in patients with multiple myeloma. There are 2 cohorts and patients will be enrolled sequentially to cohort A, then to cohort B. The sample size is 30 patients for this trial (15 for each cohort). We expect that at least 2/3 of each cohort will complete 12 cycles of maintenance panobinostat (regardless of dose modification) and will be evaluable for the primary endpoint. The widths of 95% confidence interval (CI) are 0.356, 0.438, 0.487, 0.514, and 0.522 when the proportions of patients tolerating 12 cycles of maintenance are 0.9, 0.8, 0.7, 0.6, and 0.5, respectively.

A patient who withdraws from the study due to reasons other than death, disease progression or toxicity will be replaced and is considered as non-evaluable for primary endpoint. The proportion of patients tolerating the therapy will be reported with 95% CI. All 30 patients are eligible for secondary endpoints. We will compute the overall response rates before the transplant, after autologous HCT, and after the completion of maintenance therapy, and at best response. The OS and PFS will be estimated using the Kaplan-Meier method. We will also report the incidences of all grades and grade ≥ 3 toxicities. The two-sided 95% CIs for

proportion, and OS and PFS will be computed using the Clopper-Pearson method and the Greenwood formula, respectively. In addition, the frequency of B cell precursor as well as other cell subsets, and their 95% CI will be evaluated using t-distribution. If data do not meet normality assumption, the power transformation (e.g., log-transformation) will be conducted. Those patients who are not in CR before the transplant would be most suitable for T-effector activity analysis. This will be examined by the paired t-test or the Wilcoxon signed-rank test, depending on the data distribution.

Relative dose intensity (RDI) represents the ratio of the amount of a drug actually delivered [actual dose intensity (DI)] to the amount planned (planned DI). The purpose of calculating RDI is to evaluate whether the planned DI of a chemotherapy treatment was actually achieved which may suggest the feasibility of planned treatment regimen. There are multitude of reports demonstrating a correlation between RDI and survival in cancer treatment.

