13.1.4 Secondary objective and hypothesis

The secondary objectives of the study are to evaluate following parameters in patients who receive panobinostat maintenance therapy after autologous HCT: overall response rate, best response rate, 2-year PFS and 2-year OS. The exploratory secondary objectives include evaluation of minimal residual disease, frequency of B cell precursors and immune subsets, protein acetylation, and immune response against pneumococcal vaccines and CRM. The association of minimal residual disease, B cell precursors, and immune response with response, PFS and OS will be evaluated using the Cox proportional hazards regression model.

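### Section 13.1.4 applies a Cox model to response, which has no event time in this plan, and leaves the marker draw, time origin and covariate type for PFS and OS unstated, so immortal-time bias is possible but not certain

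*Combined protocol and SAP*

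**What the plan says.** Section 13.1.4 names one method for all the marker associations: the relation of MRD, B-cell precursors and "immune response with response, PFS and OS will be evaluated using the Cox proportional hazards regression model".

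**Response.** Section 13.1 treats it as a proportion at set occasions: "We will compute the overall response rates before the transplant, after autologous HCT, and after the completion of maintenance therapy, and at best response". Section 13.1.4 lists the secondary endpoints as "overall response rate, best response rate, 2-year PFS and 2-year OS". Section 8.2 grades response by the IMWG categories of Appendix C at about cycles 3, 6, 9 and 12. Section 13.1 gives proportions Clopper-Pearson limits. No time to response is defined.

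**Markers.** One MRD objective in Section 4.2 is "To evaluate minimal residual disease (MRD) after autologous HCT followed by panobinostat maintenance therapy using flow cytometry". Section 9.3 takes marrow before transplant and later "at cycle #6 of maintenance and after completion of planned panobinostat maintenance therapy to evaluate myeloma clones". In Section 9.2, vaccine antibody is measured "at baseline, at cycle #6 and after completion of maintenance (completion of 12 cycles) to assess immune reconstitution", and T-cell response is "evaluated at baseline, after cycle #3 and cycle #6, and after completion of maintenance therapy". Tables 8-1 and 9-1 also schedule blood and marrow before maintenance.

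**Time scale.** The objective in Section 4.2 is "To determine the 2-year PFS and OS of autologous HCT followed by panobinostat maintenance therapy in patients with multiple myeloma". That suggests transplant as the origin, but no origin is stated. Section 7.1 starts maintenance between day +90 and day +180. Under Section 7.3 treatment stops at progression and is planned for 48 weeks.

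**The concern.** A Cox model needs a time to an event and a censoring rule. Response has neither here, so the analyst would have to invent an endpoint in order to follow the plan.

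For PFS and OS the issue is timing. A marker drawn at the end of maintenance exists only for patients who reach that draw. If it is treated as known from time 0, its favourable group is credited with months in which its members could not have had an event. An artefactual protective hazard ratio would look like support for the idea in Section 2.2.3 that panobinostat may clear the B-cell progenitors thought to sustain residual disease. The sentence in Section 13.1.4 contains nothing that rules this out.

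**Working it through.** **The plan's own figures.** None is given for the marker analysis. The only precision figures are the interval widths in Section 13.1 (0.356, 0.438, 0.487, 0.514, 0.522). Clopper-Pearson limits with n = 15 reproduce all five. They concern the completion rate and are not affected by this point.

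**Response.** Section 13.1.4 prescribes a hazard model. Sections 8.2, 13.1 and Appendix C supply a category at fixed visits and a proportion. No section supplies an origin, an event date or a censoring rule for response. The method and the endpoint do not match.

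**PFS: inputs.**
- N = 30 (Section 13.1).
- Last draw at 48 weeks: cycle 12 starts at week 44, and Table 8-1 puts the end-of-study visit 4 weeks later. 48 × 7 / 30.44 = 11.04 months.
- Follow-up of 24 months from first dose (an assumption; the endpoint is 2-year PFS).
- Median PFS of 23 to 46 months (an assumption). Section 1.1.1 quotes median PFS of 23 and 41 months in one maintenance trial and a median time to progression of 46 months in another.
- Exponential times, no dropout, marker favourable in 50% and unrelated to PFS (assumptions).

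**Expected PFS events** = 30 × (1 − 0.5^(t/median)).

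| Median (months) | By 24 months | Before 11.04 months | After the draw |
|---|---|---|---|
| 23 | 15.4 | 8.5 | 6.9 |
| 41 | 10.0 | 5.1 | 4.9 |
| 46 | 9.1 | 4.6 | 4.5 |

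About half of the events come before the last draw.

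**Worst-case coding by hand, median 23 months.** The end-of-maintenance marker is fixed from time 0, and patients without the sample count as unfavourable.
- Monthly hazard = ln 2 / 23 = 0.0301.
- Favourable group: 30 × 0.717 × 0.5 = 10.75 patients, none with an event before 11.04 months. Probability of an event between the draw and month 24 = 0.323, so 3.48 events. Person-months = 10.75 × (11.04 + 0.323/0.0301) ≈ 234. Rate 0.0149.
- All patients: 15.45 events in 15.45/0.0301 ≈ 512 person-months. The unfavourable group therefore has 11.97 events in about 278 person-months. Rate 0.0430.
- Rate ratio = 0.0149/0.0430 = 0.35, although the marker has no effect.

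The same steps give 0.36 at a median of 46 months.

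**Simulation under no effect** (1,000 trials of 30 per median; trials in which either marker group had no event were set aside).

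| Coding | Median HR, 23 / 46 months | False positives, 23 / 46 months |
|---|---|---|
| End-of-maintenance value fixed from time 0, unsampled counted unfavourable | 0.33 / 0.38 | 37% / 13% |
| Ever favourable at cycle 3, 6 or 12, fixed from time 0 (20% per visit) | 0.57 / 0.61 | 14% / 5% |
| Only sampled patients, timed from 0 | 0.95 / 1.03 | 1.5% / 0.2% |
| Landmark at the draw | 0.95 / 1.03 | 1.5% / 0.2% |

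The last two rows agree exactly. With a common draw time, moving the origin subtracts a constant from every time, and the Cox partial likelihood uses only the order of the times.

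**Information left after the landmark.** Detectable HR with 80% power and a 1:1 marker split = exp(−(1.96 + 0.84)/√(d/4)). For d = 9 to 15 events (the whole 24 months) it is 0.15 to 0.24. For d = 5 to 7 (after the landmark) it is 0.08 to 0.12.

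**Deaths.** Assuming the 3-year OS of 80% to 88% in Section 1.1.1 and a constant hazard, 30 × (1 − 0.80^(2/3)) = 4.1 and 30 × (1 − 0.88^(2/3)) = 2.5 deaths by 24 months. About 2.0 and 1.2 of these fall before 11.04 months.

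**The case against.** A reader might infer that the planned PFS and OS hazard ratios will carry immortal-time bias. The documents do not support that, for three reasons.

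- Section 13.1.4 does not say that later draws are used. Pre-maintenance samples exist, and a pre-maintenance marker timed from first dose carries no immortal time.
- Landmark and time-dependent analyses are themselves Cox analyses and fit the sentence.
- The hazard ratio near 0.35 needs unsampled patients to be counted as unfavourable. No section prescribes this; the natural reading of the schedule is that their values are missing.

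All three stand. So does the remark that the PFS figures cannot be carried over to OS, where too few deaths are expected, and that the low false-positive rate of the landmark partly reflects how little information it has.

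What does not follow is that nothing needs saying. The MRD objective concerns disease status after maintenance, treatment stops at progression, and the plan expects only at least two-thirds of patients to complete. If that expectation is just met, 10 of 30 patients may lack the final sample, and the analyst must decide how to handle them. If transplant is the origin, even the pre-maintenance draw follows a stretch of guaranteed event-free time.

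The objection that these are exploratory analyses in 30 patients limits the weight of the point. It does not repair the method named for response.

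**Conclusion.** The point about response holds in full: a Cox model is named for an outcome that has no event time in this plan.

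For PFS and OS the defect is under-specification with a conditional risk. In the worst-case coding, the null PFS hazard ratio is about 0.33 to 0.38, with false positives of roughly 13% to 37%. Fixed coding of ever-favourable values gives 0.57 to 0.61. With only sampled patients and a common draw time there is no bias. These sizes rest on exponential PFS, assumed medians of 23 to 46 months, 24 months of follow-up, no dropout, and marker prevalence of 50% (20% per visit for the ever coding). No bias was computed for OS.

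The completion-rate and dose-intensity analyses are untouched. The correction is worth making before the marker data are analysed, mainly because it costs so little.

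**What to change.** Replace the sentence in Section 13.1.4 with wording that does the following.

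1. Response: compare marker levels between response categories with an exact or Wilcoxon test, or use logistic regression. Name the response assessment used.
2. PFS and OS: state the time origin. Enter pre-maintenance markers as fixed covariates timed from first dose.
3. Later markers: use a landmark at the draw, restricted to patients event-free and sampled by then, or a time-dependent covariate. State that a missing sample is not an unfavourable result.
4. Report end-of-maintenance landmark results as descriptive.

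Also reconcile the cycle 6 marrow sample, which Section 9.3 describes but Tables 8-1 and 9-1 omit, because it decides whether an earlier marrow landmark is available.

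The cost is wording only, with no added visits or patients. The downside is that the end-of-maintenance landmark keeps only about 5 to 7 PFS events and, on the OS assumption above, about one or two deaths. It cannot settle whether a marker is prognostic.

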13.1.5 Early stopping rule

No early stopping rule is considered in this study but the safety and efficacy data will be continuously monitored by PI and the supporting company (Novartis). Patient accrual will be temporarily suspended if the completion rate of maintenance therapy at the end of 12 cycles is equal to or less than 60% or if the non-hematologic grade 3 or 4 toxicity rate is 40% or higher. The PI and the supporting company (Novartis) will review safety data, and the study may be early terminated based on the review results.

14 Procedures and instructions

14.1 Publication of results

Any formal presentation or publication of data from this trial may be published after review and comment by Novartis and prior to any outside submission. Novartis must receive copies of any intended communication in advance of publication (at least fifteen working days for presentational materials and abstracts and thirty working days for manuscripts). These requirements acknowledge Novartis' responsibility to provide peer input regarding the scientific content and conclusions of such publications or presentations. Principal Investigation/Institution shall have the final authority to determine the scope and content of its publications, provided such authority shall be exercised with reasonable regard for the interests of Novartis and, in accord with the trial contract and shall not permit disclosure of Novartis confidential or proprietary information.

14.3 Discontinuation of study

Novartis reserves the right to discontinue any study under the conditions specified in the clinical trial agreement.

15 Ethics and Good Clinical Practice

This study must be carried out in compliance with the protocol and the principles of Good Clinical Practice, as described in Novartis standard operating procedures and:

1. ICH Harmonized Tripartite Guidelines for Good Clinical Practice 1996. Directive 91/507/EEC, The Rules Governing Medicinal Products in the European Community.
2. US 21 Code of Federal Regulations dealing with clinical studies (including parts 50 and 56 concerning informed consent and IRB regulations).
3. Declaration of Helsinki and amendments, concerning medical research in humans (Recommendations Guiding Physicians in Biomedical Research Involving Human Subjects).

The investigator agrees to adhere to the instructions and procedures described in it and thereby to adhere to the principles of Good Clinical Practice that it conforms to.

15.1 Institutional Review Board/Independent Ethics Committee

Before implementing this study, the protocol, the proposed informed consent form and other information to subjects, must be reviewed by a properly constituted Institutional Review Board/Independent Ethics Committee/Research Ethics Board (IRB/IEC/REB). A signed and dated statement that the protocol and informed consent have been approved by the IRB/IEC/REB must be given to Novartis before study initiation. Any amendments to the protocol, other than administrative ones, must be reviewed by Novartis approved by this committee.

15.2 Informed consent

The investigators and/or designee (including clinical trial coordinators or advanced practice professionals) must explain to each subject (or legally authorized representative) the nature of the study, its purpose, the procedures involved, the expected duration, the potential risks and benefits involved and any discomfort it may entail. Each subject must be informed that participation in the study is voluntary and that he/she may withdraw from the study at any time and that withdrawal of consent will not affect his/her subsequent medical treatment or relationship with the treating physician.

This informed consent should be given by means of a standard written statement, written in non-technical language. The subject should read and consider the statement before signing and dating it, and should be given a copy of the signed document. If the subject cannot read or sign the documents, oral presentation may be made or signature given by the subject's legally

appointed representative, if witnessed by a person not involved in the study, mentioning that the patient could not read or sign the documents. No patient can enter the study before his/her informed consent has been obtained.

The informed consent form is considered to be part of the protocol, and must be submitted by the investigator with it for IRB/IEC/REB approval.

16 References

16.1 Appendix A: Medications requiring caution for potential drug-drug interactions

16.1.1 Medications which have a risk of causing Torsades de pointes ventricular arrhythmia should be avoided

Patients who are currently receiving treatment of the medications in [Table 17-1](#) and cannot either discontinue from this treatment or switch to an alternative medication prior to enrollment in a panobinostat clinical study, will be excluded from the study. Patients may not begin panobinostat treatment with any of the medications listed in [Table 17-1](#) unless this is discussed with the supporting company (Novartis) and an approval is granted by the supporting company (Novartis). The supporting company (Novartis) may agree to temporarily discontinue panobinostat treatment (e.g., for 72 hours) during administration with these drugs or withheld medications in [Table 17-1](#) for at least 72 hours when panobinostat is to be administered.

NOTE: It is of great importance to avoid combining drugs listed below in [Table 17-1](#) and [Table 17-2](#) (CYP3A inhibitors) especially in the presence of electrolyte abnormalities, notably decreased potassium or magnesium levels commonly associated with diuretic usage.

In general, medications listed in [Table 17-1](#) should be avoided while medications listed in [Tables 17-2](#) and [17-3](#) are to be used with caution when co-administered with panobinostat. Please select the most stringent recommendation for concomitant medications (i.e., to be avoided) which are common among the tables (e.g., erythromycin, clarithromycin)

Table 17-1 Medications which have a risk of causing Torsades de pointes to be avoided

All Class IA antiarrhythmics 
• quinidine• procainamide• disopyramide• any other class IA antiarrhythmic drug
All Class III antiarrhythmics amiodarone sotalol bretylium disopyramide dofetilide ibutilide any other class III antiarrhythmic drug

Antibiotics Macrolide antibiotics* 
• erythromycin• clarithromycin• telithromycin Quinolone antibiotics* sparfloxacin
Antipsychotics thioridazine mesoridazine chlorpromazine pimozide
Antimalarials 
• halofantrine• chloroquine
Miscellaneous drugs 
• arsenic trioxide• astemizole• bepridil• domperidone• levomethadyl• methadone• pentamidine• droperidol
*Note: azithromycin, ciprofloxacin, levofloxacin, pefloxacin, ofloxacin, tosufloxacin, difloxacin, temafloxacin, fleroxacin, acrosoxacin, nalidixic acid and enoxacin are allowed.

This is not a comprehensive list of medications which may prolong the QT interval or have a risk of causing Torsades de pointes. This list of medications was developed in collaboration with an external cardiology consultant, and represents those medications which are deemed to have an unacceptable risk of co-administration with panobinostat.

The following website may be referenced as a supplemental guide for drugs which have been associated with Torsades de pointes or prolonging the QT interval but at this point lack substantial evidence for causing Torsades de pointes:

<http://www.qtdrugs.org/medical-pros/drug-lists/drug-lists.htm#>.

Medications listed on the website which do not appear in [Table 17-1](#) above may be used with caution at the discretion of the investigators.

The serotonin (5HT₃) antagonists, often used as antiemetics, such as ondansetron, dolasetron, (also are known CYP2D6 substrates, see [Table 17-3](#)), or granisetron have been associated with Torsades de points and QT prolongation but have not been shown to cause Torsades de pointes. Therefore, 5HT₃ antagonists are not per se prohibited but close monitoring for signs and symptoms of QT prolongation is recommended. Caution is to be exercised when using these or other agents that may prolong QT intervals in combination with panobinostat.

